Appendix 4. Hepatic Monitoring Tests for Treatment-Emergent Abnormality

Selected tests may be obtained in the event of a treatment-emergent hepatic abnormality and may be required in follow-up with patients in consultation with Lilly or its designee CRP. Hepatic monitoring tests will be conducted at local laboratory or central laboratory in the case of hepatitis E.

Hepatic Monitoring Tests

Hepatic Hematology^a	Haptoglobin^a
Hemoglobin	
Hematocrit	Hepatic Coagulation^a
RBC	Prothrombin time
WBC	Prothrombin time, INR
Neutrophils	
Lymphocytes	Hepatic Serologies^{a,b}
Monocytes	Hepatitis A antibody, total
Eosinophils	Hepatitis A antibody, IgM
Basophils	Hepatitis B surface antigen
Platelets	Hepatitis B surface antibody
	Hepatitis B core antibody
Hepatic Chemistry^a	Hepatitis C antibody
Total bilirubin	Hepatitis E antibody, IgG
Conjugated bilirubin	Hepatitis E antibody, IgM
Alkaline phosphatase	
ALT	Anti-nuclear Antibody^a
AST	Alkaline Phosphatase Isoenzymes^a
GGT	Anti-smooth Muscle Antibody (or Anti-actin
CPK	Antibody)^a

Abbreviations: ALT = alanine aminotransferase; AST = aspartate aminotransferase; CPK = creatinine phosphokinase; GGT = gamma-glutamyl transferase; Ig = immunoglobulin; INR = international normalized ratio; RBC = red blood cell; WBC = white blood cell.

^a Assayed by Lilly-designated or local laboratory.

^b Reflex/confirmation dependent on regulatory requirements and/or testing availability.

Appendix 5. Blood Sampling Summary

This table summarizes the approximate number of venipunctures and blood volumes for all blood sampling (screening, safety laboratories, and bioanalytical assays) during the study.

Protocol I8R-MC-IGBI Sampling Summary

Purpose	Blood Volume per Sample (mL)	Number of Blood Samples	Total Volume (mL)
HbA1c	2	2	4
Clinical laboratory tests ^a	15	4	60
Pharmacokinetics – glucagon	4	27	108
Pharmacokinetics – DPC	4	≤11	44
Pharmacodynamics – plasma glucose	2	22	44
Exploratory sample	10	2	20
Pharmacogenetics	10	1	10
Bedside plasma glucose (SuperGL)	0.5	144 (max)	72
Total			362
Total for clinical purposes			370

^a Additional samples may be drawn if needed for safety purposes.

Appendix 6. Nasal and Non-nasal Score Questionnaire

Nasal and Non-nasal Score Questionnaire

Please select the number that corresponds best to the effects/symptoms you are experiencing at this time, or have experienced since last questioning.

0=Not experiencing this (no symptoms at all).

1=Only experiencing a mild case of this and it is easily tolerated.

2=Experiencing a moderate level of this symptom. It is bothersome but tolerable.

3=Experiencing a severe level of this symptom. It is hard to tolerate and interferes with your activities.

Symptoms	Scale			
	0 None	1 Mild	2 Moderate	3 Severe
1. Runny nose	0 None	1 Mild	2 Moderate	3 Severe
2. Nasal congestion (nostrils plugged)	0 None	1 Mild	2 Moderate	3 Severe
3. Nasal itching	0 None	1 Mild	2 Moderate	3 Severe
4. Sneezing	0 None	1 Mild	2 Moderate	3 Severe
5. Watery eyes	0 None	1 Mild	2 Moderate	3 Severe
6. Itchy eyes	0 None	1 Mild	2 Moderate	3 Severe
7. Redness of eyes	0 None	1 Mild	2 Moderate	3 Severe
8. Itching of ears	0 None	1 Mild	2 Moderate	3 Severe
9. Itching of throat	0 None	1 Mild	2 Moderate	3 Severe

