Nasal inspection		X		Nasal inspection should be conducted before the procedure to induce hypoglycemia and at 90 minutes postglucagon administration
Injection-site inspection (for IM glucagon only)		X		The injection site will be inspected before the procedure to induce hypoglycemia to confirm injection site is normal and at 90 minutes postglucagon administration
Nasal and Non-nasal Score Questionnaire		X		See Appendix 6, Nasal and Non-nasal Score Questionnaire. Questionnaire to be completed approximately 30 minutes prior to hypoglycemia induction and 15, 30, 60, and 90 minutes postglucagon administration

Edinburgh Hypoglycemia Scale		X		See Appendix 7 , Edinburgh Hypoglycemia Scale. This questionnaire should be completed when $PG \leq 75$ mg/dL and again at $PG \leq 60$ mg/dL after the start of the insulin infusion and at 15, 30, 45, and 60 minutes postglucagon administration
Insulin infusion to induce hypoglycemia		X		Refer to Sections 9.2 and 7.7 for details regarding this procedure, including steps to take before the procedure begins and steps to take if there is an insufficient response to glucagon administration. Procedures taking place on Period 2 will occur at approximately the same time as those for Period 1.
Study drug administration		X		Once PG reaches below 60 mg/dL, the insulin infusion is stopped and approximately 5 minutes later study drug is administered
Sample collection for measurement of glucagon		X	X	Samples will be collected pre-dose (i.e., immediately prior to glucagon administration) and at 5, 10, 15, 20, 25, 30, 40, 50, 60, 90, 120, and 240 minutes post-glucagon administration at Periods 1 and 2 and once at follow-up. All samples will be processed at a central laboratory.
Sample collection for measurement of DPC		X		Samples will be collected from NG-treated patients pre-dose (i.e., immediately prior to glucagon administration) and at 10, 20, 30, 40, 60, 120, and 240 minutes post-glucagon administration. Three additional samples may be collected. Samples to be processed at a central laboratory.

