3.3. Benefit–Risk Assessment

Glucagon is generally well tolerated, with mild side effects noted. These included occasional nausea and vomiting; however, these side effects may also occur with hypoglycemia (for example, dizziness, fainting, light headedness, blurred vision, headaches, fatigue). Nasal glucagon is a needle-free, ready-to-use nasal dosing device for administration into nostrils requiring no inhalation. In contrast to other products on the market, this requires no reconstitution. Patients being treated with the investigational product will derive no direct benefit from it as treatment will follow an insulin-induced hypoglycemia.

To date, there have been 10 completed clinical studies (8 in adults, 2 in pediatric population) in which the safety, efficacy, or effectiveness of NG has been evaluated. No deaths or serious adverse events (SAEs) associated with NG occurred during these studies. The most frequently reported treatment-emergent adverse events (TEAEs) in NG-treated patients represent events related to local tolerability including lacrimation increased, headache, rhinorrhea, nasal discomfort, nasal congestion, and nasal pruritus, and gastrointestinal disorders including nausea and vomiting. All TEAEs were transient in nature and most resolved within 24 hours of exposure. Severe adverse reactions to glucagon are very rare, although generalized allergic reactions, urticaria, respiratory distress, and hypotension have been reported in patients who have received glucagon.

This study will expose patients with T1DM to an insulin-induced hypoglycemia meant to simulate hypoglycemia in a controlled setting. The protocols used to induce the controlled hypoglycemia have been adopted from a previously completed trial, specifically Study IGBC, that demonstrated the safe use of this method. This is an inpatient procedure in which the patients will be under constant supervision of the clinical research unit (CRU) staff. Safety provisions have been considered in that IV glucose will be administered if the patient

experiences signs and symptoms of severe hypoglycemia and gauged to require intervention during the experimental procedure, at the discretion of the investigator.

No clinically significant safety or tolerability concerns have been identified in patients to date for NG up to the highest single dose (6-mg) given in an acute setting.

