5.1. Overall Design

This is a Phase 1, multicenter, randomized, open-label, 2-treatment, 2-period, crossover study. [Figure IGBI.1](#) illustrates the study design. In each period, patients with T1DM will undergo a procedure to induce hypoglycemia using insulin infusion. The insulin infusion will be used to decrease PG and will be stopped once PG <60 mg/dL and it is expected that PG will continue to decrease for an additional 15 to 20 mg/dL to its lowest concentration. Approximately 5 minutes after the insulin infusion is stopped, patients will be administered either 3-mg NG (LY900018) or 1-mg IMG (GlucaGen) in the deltoid muscle of the nondominant arm by CRU staff members. Serial blood sampling will be performed for glucagon and PG concentration assessments immediately before and up to 6 hours following administration of glucagon. Following each test period, patients will remain in the CRU for at least 6 hours following the procedure. All patients will receive a carbohydrate-rich meal prior to discharge. Patients may stay longer as needed, at the discretion of the investigator.

After a wash-out period of at least 1 day (24 hours) and no more than 7 days, patients will return to the clinic and the procedure repeated with each patient crossed over to the alternate glucagon treatment.

A CRU visit for follow-up or early discontinuation should occur approximately 28±2 days after the last dose of study drug.

Abbreviations: CRU = clinical research unit; IM = intra-muscular; T1DM = type 1 diabetes mellitus.

Figure IGBI.1. Illustration of study design for Protocol I8R-MC-IGBI.

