5.4. Scientific Rationale for Study Design

This study will be used to supplement the comprehensive chemistry, manufacturing control analytical plan for bridging the planned commercial drug product with the clinical trial drug product. Since the existing stores of clinical trial drug product have been exhausted, an indirect comparator/bridging study must be performed to demonstrate efficacy comparability.

This study design involves an open-label assessment of the planned commercial drug product compared to the marketed product (GlucaGen) within the T1DM population. The 2 study periods will be separated by a washout period of no less than 1 day (24 hours) and no more than 7 days due to the short half-life of NG (approximately $t_{1/2} = 25$ minutes). The second of the 2 study periods will expose the same patients to the alternate study arm (for example, those randomly assigned to receive NG LY900018 will receive IM GlucaGen for Period 2). This crossover design will allow each individual patient to act as an internal control.

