10.3.2.2. Nasal and Non-nasal Score Questionnaire

The scoring for each response to Nasal and Non-nasal Score Questionnaire will follow the scale displayed on the questionnaire ('None'=0, 'Mild'=1, 'Moderate'=2, 'Severe'=3). The total score of the questionnaire will be calculated as the sum of the scores for each question. Descriptive statistics will be used to summarize the baseline, various postdose time points, and absolute change from baseline in total score of Nasal and Non-nasal Score Questionnaire by treatment group. See [Appendix 6](#) for a copy of the questionnaire. Additional analysis will be performed if deemed necessary. The details will be provided in the SAP.

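### The nasal questionnaire's recall clause also governs the Period 2 baseline form, so resolved nasal-glucagon symptoms can enter the GlucaGen baseline and modestly distort change from baseline

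*Protocol*

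**What the plan says.** Appendix 6 gives a single instruction for the form. The patient rates "effects/symptoms you are experiencing at this time, or have experienced since last questioning". Nine symptoms are each scored 0 to 3, with anchors in the present tense, for example "0=Not experiencing this (no symptoms at all". No separate wording is given for the pre-induction form.

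The Schedule of Activities (Section 2) applies one timetable to both periods: "Questionnaire to be completed approximately 30 minutes prior to hypoglycemia induction and 15, 30, 60, and 90 minutes postglucagon administration". Section 5.1 separates the periods: "After a wash-out period of at least 1 day (24 hours) and no more than 7 days". Section 5.4 confirms the crossover: "those randomly assigned to receive NG LY900018 will receive IM GlucaGen for Period 2".

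Section 10.3.2.2 sums the item scores. It plans descriptive summaries of the baseline score, the post-dose scores and "absolute change from baseline in total score of Nasal and Non-nasal Score Questionnaire by treatment group". It does not say whether baseline is taken afresh in each period.

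Section 3.3 names the commonest NG events as "local tolerability including lacrimation increased, headache, rhinorrhea, nasal discomfort, nasal congestion, and nasal pruritus", together with gastrointestinal events, and says of their duration: "All TEAEs were transient in nature and most resolved within 24 hours of exposure".

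**The concern.** A baseline score should describe the patient just before the procedure. Here the same word covers two different quantities. In Period 1 there is no earlier form, so the baseline can only be the current state. In Period 2 the last scheduled form is the 90-minute form of Period 1, so the recall clause opens a window of one to seven days.

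That window falls straight after the first product. Runny nose, congestion, nasal itching and watery eyes are form items, and Section 3.3 lists the corresponding events as frequent after NG. In an NG-first patient, any of these that lasted beyond 90 minutes may be scored on the Period 2 baseline form although it has gone. That score is then subtracted from the GlucaGen post-dose scores.

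At stake is one view of comparative nasal tolerability. Safety and tolerability versus GlucaGen is the first secondary objective. Sections 9.3.1.2 and 10.3.2.1 send nonserious events elicited by this questionnaire to a separate analysis, which is the score in Section 10.3.2.2.

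**Working it through.** The protocol states no figure for this point, so there is none to reproduce. The check has four steps.

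**1. Length of the look-back.** Inputs: last Period 1 form at 90 minutes = 1.5 h (Schedule of Activities); washout 24 h to 7 days = 168 h (Section 5.1). The small offset for the timing of induction is ignored.

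- Shortest: 24 - 1.5 = 22.5 h.
- Longest: 168 - 1.5 = 166.5 h.
- For comparison, the 30-, 60- and 90-minute forms look back 15, 30 and 30 minutes.
- The Period 1 baseline has no previous form.

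**2. One illustrative record (invented scores).** An NG-first patient has a mild runny nose (1) and mild congestion (1) that last to 2 hours after NG and are gone before Period 2. All GlucaGen post-dose scores are 0.

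- Period 2 baseline as worded: 1 + 1 = 2. Change: 0 - 2 = -2.
- Period 2 baseline on current symptoms: 0. Change: 0 - 0 = 0.

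**3. What cancels between sequences.** Both sequences have the long look-back in Period 2. Assume half the patients are in each. Let b be the mean recalled score from ordinary washout symptoms (colds, allergy), and r(NG) and r(IM) the mean recalled scores from residual effects of each product.

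- Shift in mean GlucaGen change: -0.5 x (b + r(NG)), from NG-first patients.
- Shift in mean NG change: -0.5 x (b + r(IM)), from GlucaGen-first patients.
- Shift in the contrast, NG minus GlucaGen: 0.5 x (r(NG) - r(IM)).

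The ordinary symptoms b drop out. Only NG's excess residual symptoms remain, and if r(NG) exceeds r(IM) they make NG look relatively worse.

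**4. Size.** Write r(NG) = p x s, where p is the share of NG-first patients whose symptoms outlast the 90-minute form and are scored on recall, and s is their mean recalled score. Neither is in the protocol. The part of the shift in mean GlucaGen change that is due to NG is -0.5 x p x s:

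| p | s = 1 | s = 2 | s = 3 |
|---|---|---|---|
| 0% | 0 | 0 | 0 |
| 10% | -0.05 | -0.10 | -0.15 |
| 20% | -0.10 | -0.20 | -0.30 |
| 40% | -0.20 | -0.40 | -0.60 |

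Within NG-first patients alone the values are twice these, up to -1.2. The total runs from 0 to 9 x 3 = 27, so 0.05 to 0.6 points is about 0.2% to 2.2% of the range. If r(IM) is taken as 0, the contrast shifts by the same amounts with the opposite sign.

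**The case against.** **Which questioning is the last one?** Section 9.3.1.2 has staff ask about adverse events before giving this form. On that reading the look-back at the Period 2 baseline is minutes, not days. But the same questioning is prescribed before the form without limitation to baseline, so the reading would shrink the look-back to minutes every time and leave the recall clause with almost nothing to do. It shows that the stem is ambiguous, not that the baseline is sound. The present-tense anchors likewise may lead some patients to ignore the clause, which reduces p but not reliably to zero.

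**The consequences are limited.** This stands. Section 10.3.2.2 is descriptive, with no test, margin or decision rule. It already plans the absolute post-dose scores by treatment, which subtract no baseline, and the baseline scores themselves, where contamination could show. Spontaneously reported nasal and respiratory events are summarised separately under Section 10.3.2.1.

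**The size is assumed.** This also stands. Section 3.3 describes the duration of all treatment-emergent events together. It gives no rate for questionnaire symptoms lasting beyond 90 minutes, so the effect may be close to zero.

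**The SAP may define baseline.** It may, and taking baseline per period is the natural reading rather than a stated rule. But no SAP rule can separate current from recalled symptoms once a single score has been recorded.

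**Stronger inferences.** A reader might infer that every GlucaGen patient shows a false improvement, that only the GlucaGen baseline has the long look-back, or that the nasal safety comparison as a whole is compromised. The protocol supports none of these. NG's residual symptoms enter only through NG-first patients who have and recall them, the NG baseline in the other sequence has the same window, and the unadjusted scores are available.

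**Conclusion.** The point holds as a minor defect in an instrument. The stem fixed in Appendix 6, with the schedule and the washout, gives the Period 2 baseline a different meaning from the Period 1 baseline. The resulting error has a direction: it lowers GlucaGen's change from baseline and overstates NG's relative nasal burden, so it does not conceal harm from NG.

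The shift in mean GlucaGen change lies between 0 and -0.6 points on a 27-point total over the range examined. This rests on five assumptions: equal sequences, a baseline taken in each period, literal use of the recall clause, negligible residual nasal effect of GlucaGen, and values of p and s that the protocol does not supply. The damage is confined to the descriptive change-from-baseline summary of a secondary safety measure.

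**What to change.** - In Appendix 6, word the pre-induction form in both periods to ask only about symptoms present at that moment. Keep the recall clause on the 15-, 30-, 60- and 90-minute forms.
- In Section 10.3.2.2, state that baseline is the pre-induction score of the same period.
- If Period 2 baselines have already been collected with the present stem, rely on the absolute post-dose scores already planned for the treatment comparison, and say why.

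The cost is a line of text in each place, with no added visits, samples or patients. Symptoms still present at the Period 2 visit would continue to count, as they should. The one loss is that symptoms arising and resolving between visits would no longer be caught on this form. The adverse-event questioning in Section 9.3.1.2 still seeks them.

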Appendix 7. Edinburgh Hypoglycemia Scale

Edinburgh Hypoglycemia Scale

Each of the 13 symptoms will have a score of 1 to 7:

1 = not experiencing this (no symptoms at all).

2 = only experiencing a very mild case of this and it is easily tolerated.

3 = only experiencing a mild case of this and it is tolerated.

4 = experiencing a mild to moderate case of this and it is tolerated.

5 = experiencing a moderate case of this and it is tolerated.

6 = experiencing a moderate to severe level of this symptom. It is bothersome but tolerable.

7 = experiencing a severe level of this symptom. It is hard to tolerate.

Neuroglycopenic symptoms

Cognitive dysfunction

Inability to
concentrate:

1	2	3	4	5	6	7
						
No symptom			mild to moderate symptom			severe symptom

Blurred vision:

1	2	3	4	5	6	7
						
No symptom			mild to moderate symptom			severe symptom

Anxiety:

1	2	3	4	5	6	7
						
No symptom			mild to moderate symptom			severe symptom

Confusion:

1	2	3	4	5	6	7
						
No symptom			mild to moderate symptom			severe symptom

Difficulty speaking:

1	2	3	4	5	6	7
						
No symptom			mild to moderate symptom			severe symptom

Double vision:

1	2	3	4	5	6	7
						
No symptom			mild to moderate symptom			severe symptom

Neuroglycopenia

Drowsiness:

1	2	3	4	5	6	7
						
No symptom			mild to moderate symptom			severe symptom

Tiredness:

1	2	3	4	5	6	7
						
No symptom			mild to moderate symptom			severe symptom

Hunger:

1	2	3	4	5	6	7
						
No symptom			mild to moderate symptom			severe symptom

Weakness:

1	2	3	4	5	6	7
						
No symptom			mild to moderate symptom			severe symptom

Autonomic symptoms

Sweating:

1	2	3	4	5	6	7
						
No symptom			mild to moderate symptom			severe symptom

Trembling:

1	2	3	4	5	6	7
						
No symptom			mild to moderate symptom			severe symptom

Warmness:

1	2	3	4	5	6	7
						
No symptom			mild to moderate symptom			severe symptom

Appendix 8. Clarke Hypoglycemia Awareness Survey

Clarke Hypoglycemia Awareness Survey

Check the category that best describes you: (check one only)

	I always have symptoms when my blood sugar is low	A
	I sometime have symptoms when my blood sugar is low	R
	I no longer have symptoms when my blood sugar is low	R

2. Have you lost some of the symptoms that used to occur when your blood sugar was low:

	Yes	R
	No	A

3. In the past six months, how often have you had moderate hypoglycemia episodes? (*Episodes where you might feel confused, disoriented or lethargic and were unable to treat yourself*)

	Never	A
	Once or twice	R
	Every other month	R
	Every month	R
	More than once a month	R

4. In the past year, how often have you had severe hypoglycemic episodes? (*Episodes where you were unconscious or had a seizure and needed glucagon or intravenous glucose*)

	Never	A		5 times	R		10 times	R
	1 time	R		6 times	R		11 times	R
	2 times	R		7 times	R		12 times or more	R
	3 times	R		8 times	R			
	4 times	R		9 times	R			

5. How often in the last month have you had readings <70 mg/dL (3.9 mmol/L) with symptoms?

	Never		1 time/week		4 to 5 times/week
	1 to 3 times		2 to 3 times/week		Almost daily

6. How often in the last month have you had readings <70 mg/dL (3.9 mmol/L) without symptoms?

	Never		1 time/week		4 to 5 times/week
	1 to 3 times		2 to 3 times/week		Almost daily

If answer to question 5 < answer to question 6	R
If answer to question 6 < answer to question 5	A

7. How low does your blood sugar need to go before you feel symptoms?

	60-69 mg/dL;	3.3-3.8 mmol/L	A
	50-59 mg/dL;	2.8-3.3 mmol/L	R
	40-49 mg/dL;	2.2-2.7 mmol/L	R
	Less than 40 mg/dL;	less than 2.2 mmol/L	R

8. To what extent can you tell by your symptoms that your blood sugar is low?

	Never	R
	Rarely	R
	Sometimes	R
	Often	A
	Always	A

Abbreviations: A = aware; R = reduced awareness.

Final Score: Total Number of “R” responses. Reduced awareness = 4 or more reduced responses; Intermediate = 3 reduced responses; Aware = 2 or fewer reduced responses.

**Appendix 9. Protocol Amendment I8R-MC-IGBI(b)
Summary: Comparison of Glucagon Administered by
Either the Nasal (LY900018) or Intra-muscular
(GlucaGen®) Routes in Adult Patients with Type 1
Diabetes Mellitus During Controlled Insulin-Induced
Hypoglycemia**

Overview

Protocol I8R-MC-IGBI, Comparison of Glucagon Administered by Either the Nasal (LY900018) or Intra-muscular (GlucaGen®) Routes in Adult Patients with Type 1 Diabetes Mellitus During Controlled Insulin-Induced Hypoglycemia, has been amended. The new protocol is indicated by Amendment (b) and will be used to conduct the study in place of any preceding version of the protocol.

The amendment is in response to regulatory feedback. The overall changes made to this protocol are as follows:

- In Section 6.2 (Exclusion Criteria), criterion [23] was revised to exclude patients with current stable psychiatric disorders.
- In Section 9.2.3 (Procedures for Insufficient Response to Glucagon Administration), text was added to clarify that continuous venous access will be used to enable immediate delivery of glucose to patients if needed.
- In Section 9.3 (Adverse Events), text was added to clarify that all AEs will be documented, not just those deemed to have a causal relationship with the investigational product or those that are severe or medically important. In addition, text was added to clarify that the follow-up for all AEs should not be interrupted, even if there is a reasonable explanation for the event.

Additional clarifications were made to the bedside glucose safety measurement thresholds.

Revised Protocol Sections

Note: All deletions have been identified by strikethroughs. All additions have been identified by the use of underline.

Schedule of Activities

Procedure	Screening Visit	Period 1 and Period 2 CRU Visits	Follow-up (or ED) Visit	Comments
	Up to 28 days before Period 1	Day 1	28(\pm 2) days after last dose of study drug	
Bedside glucose safety measurements (SuperGL laboratory analyzer)		X		Samples will be collected throughout the study procedure. During the hypoglycemia induction procedure, plasma glucose concentration will be measured no more than 10 minutes apart while the plasma glucose concentration is ≥ 100 mg/dL and no more than 5 minutes apart when the plasma glucose concentration is < 100 mg/dL. Post-glucagon administration, plasma glucose concentration will be measured every 5 minutes for the first 30 minutes and every 10 minutes up to 90 minutes.

